#### 6.2.3.1.2.1 Subjects < 2 Years of Age

The initial dose of cinacalcet and all subsequent doses will be calculated by the site staff and confirmed by the IVR/IWR system.

For subjects with > 14 days since the last dose of cinacalcet treatment in Study 20110100 and day 1 of Study 20140159, subjects will start at the initial cinacalcet dose of 0.20 mg/kg/day, based on the subject's dry weight at day 1, in the 20140159 study rounded down to the lowest PSD.

#### CONFIDENTIAL

# Page 30 of 79

For subjects with  $\leq$  14 days between the last dose of cinacalcet in Study 20110100 and Study 20140159 day 1, subjects will continue the same dose of cinacalcet they received at the completion EOIP visit or early termination visit at Study 20110100 termination and follow the weekly dose adjustments outlined in Table 2. Dose titration cannot occur until week 4. If subjects from the Study 20110100 are on a dose withhold at day 1 of Study 20140159, the iPTH and cCa restart values (iPTH > 150 pg/mL and cCa > 9.0 mg/dL) must be reached prior to resuming cinacalcet in the Study 20140159.

Dose adjustments for subjects receiving cinacalcet will be assessed at each weekly visit during the treatment period. The daily dose of cinacalcet may only be increased at monthly titration visits (week 4, 8, 12, 16, 20, and 24); it can't be increased at any other time during the treatment period. At all weekly visits (including week 4, 8, 12, 16, 20, and 24), the dose may be maintained, reduced or withheld based upon the criteria in Table 2.

If any of the criteria for dose withholding are met at any time during the trial, including between scheduled study visits (ie, unscheduled), the dose of cinacalcet is to be withheld until all of the following criteria are met:

- central laboratory corrected calcium value is >9.0 mg/dL
- iPTH is >150 pg/mL
- ionized calcium is >1.13 mmol/L
- subject has no symptoms of hypocalcemia
- subject doesn't have any ongoing adverse event(s) which warrant withholding of cinacalcet.

If a subject dose is being withheld, ionized calcium levels should be assessed weekly until an ionized calcium of >1.13 mmol/L is obtained, at which point, cCa and iPTH should be assessed by the central laboratory.

Once all the restart criteria above are met, cinacalcet may be restarted at one PSD below the previous dose received. Subjects receiving the lowest PSD (1 mg) who require a dose reduction will have their dose withheld until the criteria for maintaining or increasing the dose are met, at which time they will restart dosing at 1 mg/day.

If subjects require temporary administration of concomitant medications that are known to prolong the QTc interval, are CYP3A4 inhibitors, or are CYP2D6 substrates, the administration of IP is to be withheld. The dose may be restarted at one PSD below the previous dose once the treatment with the concomitant medication has completed and all of the restart criteria above are met.

Page 32 of 79

If IP has been withheld or missed for more than 14 days, the subject will resume dosing at the starting dose level (initial dose in parent Studies 20130356 or 20110100) once all restart criteria are met.

If any of the criteria for dose decrease are met between scheduled study visits, the dose of cinacalcet is to be suspended until the next visit at which time the dose will be decreased per dose adjustment procedures of that visit.

CONFIDENTIAL

	Monthly Dose Titration Visit Rules (Weeks 4, 8, 12, 16, 20, 24)				Weekly Dose Adjustment Visit Rules (Weeks 1, 2, 3, 5, 6, 7, 9, 10, 11, 13, 14, 15, 17, 18, 19)			Dose Withholding for Safety at Any Time (Monthly, Weekly or Unscheduled)
	↑ one PSD	Maintain Dose	↓ one PSD**	withhold*	Maintain Dose	↓ one PSD**	withhold*	withhold*
	(if all c riteria met)	(if al l criteria met)	(if any criteria met)	(if any criteria met)	(if al l criteria met)	(if any criteria met)	(if any criteria met)	(if any criteria met)
Corrected Calcium (central laboratory)	≥ 9.0 mg/dL	≥ 9.0 mg/dL	≥ 8.6 - < 9.0 mg/dL	< 8.6 mg/dL	≥ 9.0 mg/dL	≥ 8.6 - < 9.0 mg/dL	< 8.6 mg/dL	< 8.6 mg/dL
	(≥ 2.25 mmol/L)	(≥ 2.25 mmol/L)	(≥ 2.15 - < 2.25 mmol/L)	(< 2.15 mmol/L)	(≥ 2.25 mmol/L)	(≥ 2.15 - < 2.25 mmol/L)	(< 2.15 mmol/L)	(< 2.15 mmol/L)
lonized Calcium	≥ 1.13 mmol/L	≥ 1.13 mmol/L	≥ 1.08 - < 1.13 mmol/L	< 1.08 mmol/L	≥ 1.13 mmol/L	≥ 1.08 - < 1.13 mmol/L	< 1.08 mmol/L	< 1.08 mmol/L
Total Calcium (local aboratory)	Not Applicable	< 8.6 mg/dL (< 2.15 mmol/L)	Not Applicable	< 8.6 mg/dL (< 2.15 mmol/L)	< 8.6 mg/dL (< 2.15 mmol/L)	Not Applicable	< 8.6 mg/dL (< 2.15 mmol/L)	< 8.6 mg/dL (< 2.15 mmol/L)
PTH	≥ 300 pg/mL 31.8 pmol/L)	≥ 150 - < 300 pg/mL (≥ 15.9 - < 31.8 pmol/L)	≥ 100 - < 150 pg/mL (≥ 10.6 - < 15.9 pmol/L)	< 100 pg/mL (≥ (< 10.6 pmol/L)	≥ 150 - < 300 pg/mL (≥ 15.9 - < 31.8 pmol/L)	≥ 100 - < 150 pg/mL (≥ 10.6 - < 15.9 pmol/L)	< 100 pg/mL (< 10.6 pmol/L)	< 100 pg/mL (< 10.6 pmol/L)
Symptoms of Hypocalcemia	None	None	N/A	Yes	None	N/A	Yes	Yes
Other AE that warrants IP dose withhold	None	None	N/A	Yes	None	N/A	Yes	Yes

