# 3.1.2 Subjects From Study 20110100

Eligible subjects will complete the End of Study visit or early termination visit for Study 20110100 and continue or restart cinacalcet treatment in this study on day 1 based on dosing instructions outlined in Section 6.2.3. Eligible subjects completing the full treatment period in Study 20110100 will be screened during the safety follow-up period in Study 20110100 and will be required to have their 20140159 day 1 visit and their 20110100 week 26 End of Study visit at the same visit. Eligible subjects who reach Study 20110100 termination before week 26 will not complete the safety follow-up period in Study 20110100, beginning the 20140159 extension study at the 20110100 early termination visit. The early termination/EOS visit in Study 20110100 and day 1 in Study 20140159 will be the same visit unless there is an administrative delay.

Subjects will complete day 1 assessments (Section 7.1) and confirm eligibility in IVR system before being dispensed IP on day 1.

Eligible subjects will continue cinacalcet treatment on day 1 based on their dry weight at the time of enrollment in 20140159 study if their iPTH is  $\geq$  150 pg/mL and cCa is  $\geq$  8.8 mg/dL (age < 2 years of age) or cCa is  $\geq$  8.4 mg/dL (age is  $\geq$  2 years of age) during screening in Study 20140159. If IP has been withheld or missed for > 14 days at the time of day 1 of Study 20140159, the subject will resume dosing at the starting dose level based on dry weight at the time of enrollment once all restart criteria are met. Cinacalcet dosing will follow the dose titration, dose withhold, and restarting rules defined in Section 6.2.3.1.2.

All subjects from 20110100 will be eligible to titrate the cinacalcet dose at monthly titration visits (beginning at week 4) to a maximum dose of 2.5 mg/kg/day based on the subject's dry weight at day 1 in Study 20140159, not to exceed a dose of 60 mg/day.

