# 6.2.3.1.2 Subjects From Study 20110100

For subjects where the last dose of cinacalcet treatment in Study 20110100 and day 1 of Study 20140159 occurs within 14 days, in order to commence dosing, subjects from Study 20110100 will follow the weekly dose adjustment criteria as outlined in Table 2 for age < 2 years and Table 3 for age  $\geq$  2 years. Dose titration cannot occur until week 4.

For subjects with > 14 days and < 1 month between last dose of cinacalcet treatment in Study 20110100 and day 1 of Study 20140159, in order to commence dosing at the initial dose, all subjects from Study 20110100 must meet restart criteria per weekly dose adjustment criteria as outlined in Table 2 for age < 2 years and Table 3 for age  $\geq$  2 years. Dose titration cannot occur until week 4.

- Additionally the phosphorus value within 7 days of day 1 should be:
  - ≥ 5.0 mg/dL (1.25 mmol/L) if age is < 1 year

  - $\ge 4.5 \text{ mg/dL} (1.13 \text{ mmol/L}) \text{ if age is } \ge 1 \text{ year}$

For subjects with > 1 month between last dose of cinacalcet treatment in Study 20110100 and day 1 of Study 20140159, in order to commence dosing, subjects from Study 20110100 must have:

- ionized calcium prior to initiation of treatment on day 1 in this study
  - $\ge 1.13 \text{ mmol/L}$  if age is < 2 years
  - ≥ 1.05 mmol/L if age is ≥ 2 years
- iPTH value ≥ 300 pg/mL within 7 days of day 1
- corrected calcium value within 7 days of day 1
  - ≥ 9.4 mg/dL if age is < 2 years

  - $\ge 8.8 \text{ mg/dL}$  if age is  $\ge 2 \text{ years}$
- phosphorus value within 7 days of day 1
  - ≥ 5.0 mg/dL (1.25 mmol/L) if age is < 1 year

  - ≥ 4.5 mg/dL (1.13 mmol/L) if age is ≥ 1 year

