#### CONFIDENTIAL

Page 52 of 79

**AMGEN**°

Table 5 below outlines the specific analytes that will be assessed at the central laboratory:

	Table 5. Analytes					
Serum Chemistry	Hematology					
Bicarbonate	Hemoglobin					
Blood Urea Nitrogen	Hematocrit					
Chloride	Platelets					
Creatinine	White blood cell count					
Potassium	Red blood cell count					
Sodium	Liver Function Tests					
Total Protein	ALT					
Total Bilirubin	AST					
Phosphorus	Alk Phos					
Other						

Table 5 Analytes

iPTH, Albumin, Calcium

Serum Pregnancy (females of child bearing potential)

Corrected Calciuma

Total and bioavailable testosterone (male)

BALP, NTx, CTx, P1NP, 25(OH) Vitamin D, FGF23 (not required for subjects from 20110100)

a Corrected calcium will be determined by the central laboratory using the following formula, where 4.0 represents the average albumin level. No correction will be made if the

serum albumin level is  $\geq$  4.0 g/dL.

Corrected calcium (mg/dL) = Measured total serum calcium (mg/dL) + 0.8 (4.0-serum albumin [g/dL])

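### Several dosing thresholds for Study 20110100 children are wrong as printed: three Maintain cells and the weekly header of Table 2, and four phosphorus limits in mmol/L

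*Protocol*

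**What the plan says.** **Table 2 (Protocol 6.2.3.1.2.1, children under 2 years).** For local total calcium, both Maintain columns, where all criteria must hold, print "< 8.6 mg/dL (< 2.15 mmol/L". All three withhold columns, where any one criterion suffices, print the same value. Tables 1 and 3 print N/A under Maintain. The weekly Maintain cell for iPTH reads "≥ 150 - < 300 pg/mL (≥ 15.9 - < 31.8 pmol/L", whereas Tables 1 and 3 print ≥ 150 pg/mL with no upper limit. The weekly block is headed "Weeks 1, 2, 3, 5, 6, 7, 9, 10, 11, 13, 14, 15, 17, 18, 19"; Tables 1 and 3 carry on after week 19.

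**Text around Table 2.** Section 6.2.3.1.2.1 bars dose increases outside the monthly visits and states: "At all weekly visits (including week 4, 8, 12, 16, 20, and 24), the dose may be maintained, reduced or withheld". It covers the lowest dose separately, for subjects on that dose ("1 mg) who require a dose reduction will have their dose withheld until the criteria for maintaining or increasing the dose are met"), who then resume at 1 mg.

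**Day 1.** Section 3.1.2 says eligible children "will continue cinacalcet treatment on day 1 based on their dry weight at the time of enrollment in 20140159 study if their iPTH is" at least 150 pg/mL, with no cap. For a gap of up to 14 days, Section 6.2.3.1.2 says that "in order to commence dosing, subjects from Study 20110100 will follow the weekly dose adjustment criteria as outlined in Table 2" (Table 3 from age 2).

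**Phosphorus.** For gaps longer than 14 days, Section 6.2.3.1.2 sets minimum phosphorus values of 5.0 mg/dL (1.25 mmol/L) under 1 year and 4.5 mg/dL (1.13 mmol/L) from 1 year. It prints them twice, once for gaps under a month and once for gaps over a month.

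**The concern.** Sites calculate each dose from these tables and the IVR/IWR system confirms it, so the printed cells are the operating rule. A condition for maintaining a dose that is identical to a trigger for withholding it cannot be meant. A weekly row with no column for iPTH of 300 or more leaves out a common state: after a gap of more than a month, Section 6.2.3.1.2 requires iPTH ≥ 300 pg/mL before dosing starts. A start limit that gives different answers in its two units is not one limit.

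The setting argues for unambiguous rules. The youngest children are the ones dosed by Table 2, and Protocol 2.4 reports a pediatric death with severe hypocalcemia in which a role of cinacalcet could not be excluded.

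**Working it through.** **1. Maintain against withhold in Table 2.** Maintain requires cCa ≥ 9.0 mg/dL, ionized calcium ≥ 1.13 mmol/L, iPTH 150 to < 300 pg/mL and, as printed, local total calcium < 8.6 mg/dL. Withhold follows from local total calcium < 8.6 mg/dL alone. Three test children:

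| cCa | Ionized Ca | Local total Ca | iPTH | As printed, monthly | As printed, weekly | On the Table 1 and 3 pattern |
|---|---|---|---|---|---|---|
| 9.5 | 1.20 | 9.5 | 200 | no column | no column | Maintain at both |
| 9.5 | 1.20 | 9.5 | 400 | increase | no column | increase monthly, Maintain weekly |
| 9.2 | 1.20 | 8.5 | 200 | Maintain and withhold | Maintain and withhold | withhold still triggered |

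The footnote to Protocol Table 5 gives "Corrected calcium (mg/dL) = Measured total serum calcium (mg/dL) + 0.8 (4.0-serum albumin [g/dL", applied when albumin is below 4.0. If local and central total calcium agree, cCa ≥ 9.0 with total calcium < 8.6 needs a correction above 9.0 − 8.6 = 0.4 mg/dL. Since 0.4 / 0.8 = 0.5, albumin must be below 4.0 − 0.5 = 3.5 g/dL. At 3.5 or above, the printed Maintain set is empty; below 3.5, it coincides with withhold.

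**2. Effect on the 1 mg restart.** At iPTH 150 to < 300 the increase column is closed (it needs ≥ 300) and Maintain is unusable, so the lowest-dose restart cannot be reached when a local value is in hand. The route that remains is in the same section and in the paragraph after Table 3. After more than 14 days withheld or missed, dosing resumes at the starting dose once the restart criteria hold: cCa > 9.0 mg/dL, iPTH > 150 pg/mL, ionized calcium > 1.13 mmol/L, no symptoms, and no adverse event that warrants withholding. These have no iPTH cap and no local total calcium term. At 0.20 mg/kg, the 7 kg entry minimum gives 0.20 × 7 = 1.4 mg, and 12.5 kg gives 0.20 × 12.5 = 2.5 mg. Rounded down to a protocol dose, a child from 7 to under 12.5 kg restarts at 1 mg, the dose the lowest-dose rule would have given.

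**3. Weekly header.** Table 1 lists 21 weekly visits and Table 2 lists 15. The missing ones are weeks 21, 22, 23, 25, 26 and 27: 6 / 21 = 28.6%. Of these six, only week 23 has a scheduled central iPTH draw (Protocol Table 4).

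**4. Phosphorus conversion.** The printed ratios are 1.25 / 5.0 = 0.250 and 1.13 / 4.5 = 0.251. The protocol's calcium ratios are 2.25 / 9.0 = 2.15 / 8.6 = 2.1 / 8.4 = 2.0 / 8.0 = 0.25. Applying 0.25 reproduces the printed phosphorus figures: 5.0 × 0.25 = 1.25, and 4.5 × 0.25 = 1.125, rounded to 1.13. One factor cannot serve two elements of different atomic mass. Taking 30.974 g/mol for phosphorus (a physical constant, not given in the documents):

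- 5.0 × 10 / 30.974 = 1.61 mmol/L; 4.5 × 10 / 30.974 = 1.45 mmol/L.
- Back-converted, 1.25 × 3.0974 = 3.87 mg/dL, which is 22.6% below 5.0; 1.13 × 3.0974 = 3.50 mg/dL, which is 22.2% below 4.5.

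Phosphorus of 3.87 to < 5.0 mg/dL (under 1 year) or 3.50 to < 4.5 mg/dL (from 1 year) passes in mmol/L and fails in mg/dL.

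**5. Reach of the phosphorus limit.** Study 20110100 doses for 24 weeks, and completers have day 1 at their week 26 visit. The nominal gap is (26 − 24) × 7 = 14 days, and the limit applies only beyond 14 days. The documents do not give that study's visit window.

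**The case against.** The best defence is that little follows from these cells in practice, and much of it stands.

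- A reader might infer that a child under 2 could be dosed at low calcium. The documents do not support this: withholding applies at any time on any single criterion, including local total calcium < 8.6 mg/dL.
- A reader might infer that a child on 1 mg with iPTH 150 to < 300 has no printed way back to treatment. The rule for more than 14 days off drug supplies one, so the misprint delays restart and does not prevent it.
- Local total calcium is not in the Schedule of Assessments, and Section 7.3.11 sends all study samples except ionized calcium to the central laboratory. The Maintain conflict arises only where a site has a local value. Section 2.4 does, however, list such values as part of the dosing scheme, so the case is not empty.
- A reader might infer that iPTH ≥ 300 pg/mL at a weekly visit leads to a wrong dose. Increases are barred then, and neither reduction nor withholding is triggered, so maintaining is all that remains. The text applies Table 2 at every weekly visit, which covers the missing weeks.
- The phosphorus limit is narrow in reach. The mg/dL values come first and are not shown to be wrong, and the ionized calcium, cCa and iPTH conditions still apply.

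The defence does not make the printed thresholds right. Nor are the Table 2 cells an artefact of text extraction: the copy of Table 2 in the Amendment 2 log has the same total calcium and weekly iPTH entries. The IVR/IWR programming may already be correct, but the documents do not show it.

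**Conclusion.** The thresholds are wrong as printed and should be fixed.

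- **Local total calcium:** two Table 2 Maintain cells contradict the withhold rule. The one practical effect is a delayed restart for a child on 1 mg with iPTH 150 to < 300 pg/mL who needed a reduction, and only where a local value is available. The albumin bound of 3.5 g/dL assumes that local and central total calcium agree.
- **Weekly iPTH cell and header:** an internal inconsistency that leaves the action unchanged.
- **Phosphorus:** four mmol/L figures sit about 22% below the mg/dL limits beside them. If the mg/dL limits are the intended ones, a site working in mmol/L could start a child whom the protocol means to exclude. How many children fall in that band after a gap of more than 14 days cannot be derived from the documents.

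None of this touches the endpoints, analysis sets or planned analyses.

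**What to change.** - In Table 2, change both Maintain cells for local total calcium to N/A, as in Tables 1 and 3, or to ≥ 8.6 mg/dL (≥ 2.15 mmol/L).
- In Table 2, print ≥ 150 pg/mL (≥ 15.9 pmol/L) for weekly Maintain iPTH, and add weeks 21, 22, 23, 25, 26 and 27 to the weekly header.
- In both phosphorus lists of Section 6.2.3.1.2, print 1.61 mmol/L beside 5.0 mg/dL and 1.45 mmol/L beside 4.5 mg/dL.
- Check the IVR/IWR programming against the corrected values.

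The cost is three cells, one header and four numbers in an amendment, plus the system check. No new data are needed and the SAP does not change.

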If subjects require temporary administration of concomitant medications that are known to prolong the QTc interval, are CYP3A4 inhibitors, or are CYP2D6 substrates, the administration of IP is to be withheld. The dose may be restarted at one PSD below the previous dose once the treatment with the concomitant medication has completed and all of the restart criteria above are met.

If IP has been withheld or missed for > 14 days, the subject will resume dosing at the starting dose level once (initial dose in parent Studies 20130356 or 20110100) all restart criteria are met based on dry weight at day 1 of Study 20140159.

AMGEN

Page 28 of 79

If any of the criteria for dose decrease are met between scheduled study visits, the dose of cinacalcet is to be suspended until the next visit at which time the dose will be decreased per dose adjustment procedures of that visit.

CONFIDENTIAL

Product: Cinacalcet HCI Protocol Number: 20140159 Date: 01 June 2016 Page 29 of 79

	Monthly Dose Titration Visit Rules (Weeks 4, 8, 12, 16, 20, 24)				Weekly Dose Adjustment Visit Rules (Weeks 1, 2, 3, 5, 6, 7, 9, 10, 11, 13, 14, 15, 17, 18, 19, 21, 22, 23, 25, 26, 27)			Dose Withholding for Safety at Any Time (Monthly, Weekly or Unscheduled)
	↑ one PSD	Maintain Dose	↓ one PSD**	withhold*	Maintain Dose	↓ one PSD**	withhold*	withhold*
	(if all c riteria met)	(if al l criteria met)	(if any criteria met)	(if any criteria met)	(if al l criteria met)	(if any criteria met)	(if any criteria met)	(if any criteria met)
Corrected Calcium (central laboratory)	≥ 8.4 mg/dL	≥8.4 mg/dL	≥ 8.0 - < 8.4 mg/dL	< 8.0 mg/dL	≥ 8.4 mg/dL	≥ 8.0 - < 8.4 mg/dL	< 8.0 mg/dL	< 8.0 mg/dL
	(≥ 2.1 mmol/L)	(≥2.1 mmol/L)	(≥ 2.0- < 2.1 mmol/L)	(< 2.0 mmol/L)	(≥ 2.1 mmol/L)	(≥ 2.0- < 2.1 mmol/L)	(< 2.0 mmol/L)	(< 2.0 mmol/L)
Ionized Calcium	≥ 1.05 mmol/L	≥ 1.05 mmol/L	≥ 1.00 - < 1.05 mmol/L	< 1.00 mmol/L	≥ 1.05 mmol/L	≥ 1.00 - < 1.05 mmol/L	< 1.00 mmol/L	< 1.00 mmol/L
Total Calcium (local laboratory)	N/A	N/A	N/A	< 8.0 mg/dL (< 2.0 mmol/L)	N/A	N/A	< 8.0 mg/dL (< 2.0 mmol/L)	< 8.0 mg/dL (< 2.0 mmol/L)
iPTH	≥ 300 pg/mL	≥ 150 - < 300 pg/mL	≥ 100 - < 150 pg/mL	< 100 pg/mL	≥ 150 pg/mL	≥ 100 - < 150 pg/mL	< 100 pg/mL	< 100 pg/mL
	(≥ 31.8 pmol/L)	(≥ 15.9 - < 31.8 pmol/L)	(≥ 10.6 - < 15.9 pmol/L)	(< 10.6 pmol/L)	(≥ 15.9 pmol/L)	(≥ 10.6 - < 15.9 pmol/L)	(< 10.6 pmol/L)	(< 10.6 pmol/L)
Symptoms of Hypocalcemia	None	None	N/A	Yes	None	N/A	Yes	Yes

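### Table 2 (children under 2 years): three Maintain cells and the weekly column heading are wrong, so the weekly dosing rule does not work as printed

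*Protocol*

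**What the plan says.** Table 2 (Protocol Section 6.2.3.1.2.1) is the dose-adjustment table for subjects under 2 years. Maintain requires all listed criteria; reduce and withhold each require any one.

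- **iPTH, weekly Maintain:** "≥ 150 - < 300 pg/mL (≥ 15.9 - < 31.8 pmol/L". The same band stands in the monthly Maintain cell, where it is right because values of 300 pg/mL or more go to the increase column.
- **Local total calcium, monthly and weekly Maintain:** "< 8.6 mg/dL (< 2.15 mmol/L", identical to the three withhold cells in that row.
- **Weekly heading:** "Weeks 1, 2, 3, 5, 6, 7, 9, 10, 11, 13, 14, 15, 17, 18, 19".

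The text of the same section says "Dose adjustments for subjects receiving cinacalcet will be assessed at each weekly visit during the treatment period", and on raising the dose outside the monthly visits, "it can't be increased at any other time during the treatment period". A child who needs a reduction from the lowest dose (1 mg) has the "dose withheld until the criteria for maintaining or increasing the dose are met". Section 6.2.3.1.2 adds that children with a gap of 14 days or less, in order to start dosing, "will follow the weekly dose adjustment criteria as outlined in Table 2 for age < 2 years".

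Tables 1 and 3, for older children, print 150 pg/mL or more with no ceiling in the weekly Maintain iPTH cell, and N/A for local total calcium in both Maintain columns. Table 1's weekly heading is "Weeks 1, 2, 3, 5, 6, 7, 9, 10, 11, 13, 14, 15, 17, 18, 19, 21, 22, 23, 25, 26, 27".

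**The concern.** Sites calculate each dose from this table and the IVR/IWR system confirms it; the system's logic is not in the documents. Read literally, the table has three faults.

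1. At a weekly visit, a child with iPTH of 300 pg/mL or more, acceptable calcium, no symptoms and no other adverse event meets no column.
2. Maintain can be met only when local total calcium is below the withhold limit, so it is never met without withhold.
3. Six weekly visits that the text covers are missing from the heading.

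The first fault is not a corner case. After a gap of more than one month, Section 6.2.3.1.2 requires iPTH of at least 300 pg/mL before dosing starts, and the dose cannot rise until week 4, so such a child begins above the weekly Maintain ceiling by rule. For gaps of 14 days or less, Section 3.1.2 allows treatment to continue at 150 pg/mL or more with no upper limit, which conflicts with the capped cell.

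These children have the tightest calcium limits in the study, and Section 2.4 reports a pediatric death with severe hypocalcemia in which a role of cinacalcet could not be excluded.

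**Working it through.** The plan gives no figure to reproduce. The check applies the printed rules to every combination of laboratory bands, assuming no symptoms and no other adverse event.

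**Inputs (Table 2).** Corrected calcium: ≥ 9.0, 8.6 to < 9.0, < 8.6 mg/dL. Ionized calcium: ≥ 1.13, 1.08 to < 1.13, < 1.08 mmol/L. Local total calcium: ≥ 8.6, < 8.6 mg/dL. iPTH: < 100, 100 to < 150, 150 to < 300, ≥ 300 pg/mL. Combinations: 3 × 3 × 2 × 4 = 72.

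**Weekly columns as printed.**
- Withhold is avoided only with corrected and ionized calcium outside their lowest bands, total calcium ≥ 8.6 and iPTH ≥ 100: 2 × 2 × 1 × 3 = 12. So 72 − 12 = 60 meet withhold.
- Of those 12, reduce is avoided only with corrected calcium ≥ 9.0, ionized calcium ≥ 1.13 and iPTH ≥ 150, which leaves 2. So 10 meet reduce.
- The 2 left are acceptable calcium with iPTH 150 to < 300, and with iPTH ≥ 300. Both have total calcium ≥ 8.6 and so fail the printed Maintain cell; the second also fails on iPTH. **No action: 2 of 72.**
- Maintain is met in 1 combination (corrected calcium ≥ 9.0, ionized ≥ 1.13, total < 8.6, iPTH 150 to < 300), which also meets withhold. **Maintain as sole action: 0 of 72.**
- At iPTH ≥ 300 alone, 1 of 18 calcium combinations has no action.

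**Monthly columns as printed.** With acceptable calcium, iPTH ≥ 300 goes to increase, but 150 to < 300 fails Maintain on total calcium. **No action: 1 of 72.**

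**Effect of each correction:**

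| Corrected | Weekly, no action | Weekly, Maintain alone | Monthly, no action |
|---|---|---|---|
| Nothing | 2 | 0 | 1 |
| iPTH cell only | 2 | 0 | 1 |
| Total-calcium cells only | 1 | 1 | 0 |
| Both | 0 | 2 | 0 |

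The two faults are separate, and both need repair.

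**Local total calcium not measured.** Dropping that factor leaves 3 × 3 × 4 = 36 combinations. If an unmeasured value counts as not applicable, acceptable calcium with iPTH 150 to < 300 meets Maintain, and 1 of 36 has no weekly action (iPTH ≥ 300); monthly, 0. If it counts as not met, the figures are 2 and 1.

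**Heading.** Weeks 1 to 27 less the 6 monthly visits (4, 8, 12, 16, 20, 24) gives 21 weekly visits. Table 2 lists 15, so 21 − 15 = 6 are missing: weeks 21, 22, 23, 25, 26 and 27. Table 1 misses none.

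**Is it a PDF fault?** Unlikely. The copy of Table 2 in the Amendment 2 summary of changes, laid out differently, has the same week list and the same tally in the total-calcium row: five < 8.6 and three Not Applicable. Tables 1 and 3 each have three < 8.0 and five N/A. That copy is too broken to confirm which column each entry sits in; the current table shows that.

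**The case against.** The strongest reply is that these are copying errors with little practical effect. Several parts of it stand.

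- Local total calcium has no row in the Schedule of Assessments (Table 4), and Section 7.3.11 sends every sample except ionized calcium to the central laboratory. It is an occasional value, so the calcium fault applies less often than the 72-combination count suggests. The iPTH gap remains either way.
- iPTH is scheduled at only 6 of the 21 weekly visits (weeks 3, 7, 11, 15, 19, 23), each one week before a titration visit. But those are the values used for titration, so a child who qualifies for a monthly increase had a result above the weekly ceiling.
- Withholding applies if any criterion is met, at any time, so no child with low calcium escapes it. A child at 300 pg/mL or more with acceptable calcium would in practice stay on the same dose. No wrong dose is shown for any profile.
- The general restart list and the table footnote do not use local total calcium. For the 1 mg restart, the increase criteria also suffice, so the faulty calcium cell matters only at iPTH 150 to < 300.
- The text applies the table at every weekly visit, so the short heading is an inconsistency rather than a missing rule.
- The combinations are not weighted by how often they occur in patients.

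Section 6.2.3.1 says the rules match the parent studies. That does not settle conflicts with this protocol's own text, and Study 20110100 treats for 24 weeks, so it does not explain a stop at week 19. The objection limits how often the faults bite; it does not make the printed rules correct.

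**Conclusion.** The concern holds and should be fixed. As printed, the weekly columns of Table 2 never give Maintain as the sole action (0 of 72) and give no action in 2 of 72 combinations; the monthly columns give none in 1 of 72. These are counts of rule outcomes, not patient frequencies, and they assume local total calcium is available. The uncovered combinations are few, but they are the ordinary on-treatment state: acceptable calcium with iPTH of 150 pg/mL or more.

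The effect is confined to children under 2 from Study 20110100. Their number is not stated: SAP Section 3.2 plans 30 subjects from that study, which enrolls from 28 days to under 6 years, so it lies between 0 and 30. Sample size and error rates are not touched, and no effect on the iPTH endpoints is claimed. The intended rule can be inferred from the ban on weekly increases and from Tables 1 and 3; whether the IVR/IWR system follows that intent or the printed table cannot be seen from the documents.

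**What to change.** In Table 2:

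1. Change the weekly Maintain iPTH cell to ≥ 150 pg/mL (≥ 15.9 pmol/L), as in Tables 1 and 3.
2. Change local total calcium to Not Applicable in both the monthly and weekly Maintain columns.
3. Extend the weekly heading to weeks 21, 22, 23, 25, 26 and 27.

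Then check the IVR/IWR logic for children under 2 against the corrected table.

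The cost is three cells and one heading in an amendment or clarification letter, plus one system check. The sponsor issued superseding Amendment 3.1 only for administrative and typographical corrections in Section 10.4.4; a dosing table merits at least as much.
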